3.0 Introduction

3.1 Background and Rationale: Lymphoedema is a chronic, progressive, and debilitating condition arising from congenital abnormalities (primary) or acquired damage (secondary) to the lymphatic system.¹ A healthy lymphatic system works primarily to 1) drain a complex fluid called lymph from the tissues; 2) direct it to structures called lymph nodes which filter out cellular debris, bacteria, and toxins, and then; 3) return it to the major vessels of the venous system.¹ The lymphatic system also serves vital immunological functions such as the production of lymphocytes to defend against infection and disease. Approximately 2-3 liters of lymph is cycled daily from the bloodstream into bodily tissues and, via the lymphatic system, back into the general circulation.²

A significant proportion of patients with lymphoedema experience a worsening, ultimately irreversible limb swelling arising from the accumulation of fluids normally regulated by the lymphatic system. Enlargement of extremity proportions may be dramatic and disfiguring. Many suffer impairments in mobility and function due to the weight and bulk of a lymphoedematous limb. Complications include chronic pain, decreased range of motion, compromised immunological function and increased incidence of acute inflammatory episodes and infection.^{2,5,6,7} Psychological complications include increased anxiety, depression, negative body image/loss of body confidence, anger, frustration, sexual dysfunction.^{8,9}

Lymphoedema is an incurable but treatable condition. Growing awareness of the considerable health, economic and psychosocial consequences of this chronic disability has intensified the search for more effective management strategies.^{3,4,10-12}

The goals of lymphoedema therapy are 1) to reduce limb girth; 2) to reduce swelling by encouraging the development of collateral lymph drainage pathways and by stimulating function of intact routes (that is to improve lymph transport from the tissues); 3) to prevent re-accumulation of fluid in interstitial tissues; 4) to prevent or control infection and; 5) to reduce physical disability and psychological sequelae.^{1,13,14}

Pneumatic compression devices (PCDs) have been utilized for many years as an adjunct to home lymphoedema care. PCD treatment is intended to assist with limb volume control for patients with lymphoedema. In many cases, the aim is to simulate and potentially replace the conventional self-manual lymphatic drainage (MLD) component during Phase II of Complete Decongestive Therapy (CDT) in patients suffering from lymphoedema. The Flexitouch® system (FT) is an advanced PCD that was developed to aid in lymphoedema management at home.

Though there have been a number of publications on the use of PCD for the treatment of lower extremity lymphoedema, none have had the aim to define the optimal treatment dose with regards to pumping pressure, frequency of treatment session, and duration of the treatment session.¹⁰ Treatment duration in the literature can range from intensive treatment of 6 to 8 hours per treatment session to a less time intensive treatment regimen of as little as 30 minutes to 1 hour per session.^{15,16} Additional studies are needed to further address the optimal dose including duration and pressure.¹⁶ Tactile Systems Technology, Inc (TSTI) the makers of the Flexitouch ® system (FT) is dedicated to improving the lives of patients with lymphoedema and chronic swelling conditions through ongoing clinical research to determine optimal treatment.

Compression garments are often part of standard care for patients with lymphoedema. For the purposes of this study that is designed to evaluate the physiologic impact of pneumatic compression device dosing, the compression garment usage will not be formally evaluated. However the compression garments will be standardized across all study patients, mandating knee high compression garments with a pressure of 30–40 mmHg. If it is determined by data collection or clinical assessment that the garments variable is influencing the FT effect then the type and use of garment will be further controlled in future studies.

[figure not shown]
3.2 Device Description and Intended Use:

Flexitouch® system (Tactile Systems Technology, Inc., Minneapolis, MN, USA): The FT is a programmable, segmental, gradient pneumatic compression device which has been cleared by the FDA for market in the US (K013061, K120972), by Health Canada for market in Canada (88415) and by European Union for market in Europe (CE 0459) for the treatment of lymphoedema, primary lymphoedema, post mastectomy oedema, oedema following trauma and sports injuries, post immobilization oedema, and venous insufficiencies. Additionally, the device has been cleared to market in the US by the FDA (K062818) for reducing wound healing time as well as the treatment and assistance in healing stasis dermatitis, venous stasis ulcers, arterial ulcers and diabetic leg ulcers (Appendix A).

4.0 Study Objectives: The study objectives have been selected in this proof of principle study in order to determine if there is a difference in treatment effect across the 3 study groups when treating lower extremity lymphoedema using the Flexitouch® system.

5.0 Study Design

5.1 Overview of Study Design: This study is a 3 arm, prospective, randomised, proof of principle clinical trial to determine the optimal treatment duration for achieving a measurable physiologic effect on lower extremity lymphoedema with the Flexitouch® system (FT) as determined by bioimpedance, perometry, tonometry, ultrasound, local tissue water assessment, symptom burden and subject interview.. Each intervention arm will include 10 completed subjects for a total of 30 completed subjects.

5.2 Endpoints

The endpoints for this study include:

- Intra/extracellular fluid changes (bioimpedance)
- Limb fluid volume changes (whole and segmental) (perometry and bioimpedance)
- Superficial tissue characteristics (induration/depth and thickness of fascia) using ultrasound and tonometry.
- Tissue water assessment utilizing Moisture Meter D and Ultrasound
- Symptom assessment (MyMOP)
- Qualitative interviews
- Activity level between and post treatment (pedometer and patient log)

5.3 Safety Endpoints: Safety endpoints will include incidence and severity of complications. A clinician will assess any signs and symptoms of acute infection, DVT, cellulitis, pain or any other need for medical intervention and the possible need for a subject to discontinue the study.

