Group A: subjects will receive 12 consecutive days of treatment utilizing the following treatment regimen. The first 5 days will be in clinic (Monday through Friday) followed by self administered at home treatment for 2 days (Saturday and Sunday). The last 5 days of treatment will be in clinic ending the treatment phase on day 12 (Monday through Friday).

- One lower extremity treatment per day using program L1 with the pressure set to "normal" applying the full garment set.

Groups B & C subjects will receive 5 consecutive days of treatment in clinic (Monday through Friday) utilizing the following treatment regimens.

- Group B: Two lower extremity treatments per day (am and pm) using program L1 with pressure set to "normal" applying the full garment set.
- Group C: Two consecutive treatments 2 times a day (am and pm) using program L1 with pressure set to "normal" applying the full garment set.

In the case of bilateral lymphoedema, the leg with the largest volume will be considered the study leg. The contralateral (non study) leg will be treated in the same manner that it was being treated prior to entering the study. Limb volume measures for both legs will be collected.

At the screening visit, each subject's compression garment(s) will be assessed for clinical adequacy (Class: $\geq 20\text{mmHg}$; Age: 3 months or less) by the Principal Investigator. Subjects will be instructed to wear the compression garment(s) every day during wakeful time. Garments may be removed while bathing and overnight. The clinician will remove the subject's compression garment during device treatment. This treatment regimen is consistent with standard home care compression garment(s) treatment.

7.2 Subject Data Requirements: The following data will be collected from all subjects:

Key: B = Before Treatment A = After Treatment D = During Visit	Screening	Baseline/ Initial Treatment (D1)	Treatment (≠ D1, 5 & 12)	Day 5(All Groups) and Day 12 (Group A)
Medical History	D			
Bio Impedance		B A	B A	B A
Perometer		B A	B A	B A
Duplex U/S	B			
Interface Pressure		B	B	B
Ultrasound		B		A
Tonometry		BA	BA	BA
Moisture Meter D		B A*	B A*	B A*
Subject Interview				D
MyMOP		D		D
Activity Level		D	D	D
BMI		D	D	D
Adverse effects		A	A	A
Compliance		D	D	D

*Group C: Will have moisture meter done before the first treatment session, after the first treatment session, and then after the final treatment session of the day = 3 times total during treatment visits.

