7.4.3 Bioelectrical Impedance: A Bioimpedance Spectroscopy (BIS) device will also be used to quantify changes in intra- and extra-cellular fluid at each visit. BIS utilizes the characteristics of frequency dependent current flow to detect fluid changes. Measurements are generated by a low frequency electrical signal transmitted to the patient from the device through skin surface electrodes. The measurement is imperceptible to the subject and is not confounded by weight or muscle changes that may occur in the limbs. Appendix B contains the study procedure for bioimpedance.

7.4.4 Limb Volume Measurement: Limb volume measures will be taken at each visit for both legs of the subject. The site will conduct limb volume measurements using an optoelectronic system (Pero-System, Perometer, Appendix C). The perometer utilizes infra red light beams to measure limb volume more rapidly than the circumferential tape measure method. These systems have been validated against circumferential measures to a correlation coefficient of .977 in leg subjects.¹⁷ The perometer can be used for whole leg or segmental (upper/lower) measurements. Perometer measurement will be taken twice on each leg and the average used.

7.4.5 Tonometry: Tissue assessment/fibrosis will be evaluated with use of a tonometer at anatomically defined locations on the affected leg and on the trunk. The Tonometer is a mechanical device that gives

an indication of the resistance of tissue to compression. It is used in lymphoedema to give an estimate of the extent of pitting and fibrotic induration. Tonometry readings of the affected areas will be compared to readings taken pre-treatment intervention. Appendix D contains the Tonometer operating instructions and the body points for this trial.

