7.4.6 Tissue Ultrasound (U/S): Tissue ultrasound will be used to measure skin thickness and oedema in fixed areas of the limb and trunk at Day 1 (pre-treatment) and at the day 5 (All Groups) and day 12 (Group A) post FT treatment. Measurements will be obtained at defined anatomic locations. The aim of this is to measure and assess for changes in the tissue in the treated limb and trunk. A positive correlation has been observed between skin thickness and oedema in the affected lymphoedema arm. In addition, increases in skin thickness may also be related to development of fibrosis or other skin changes. The use of ultrasound has been suggested in the literature as another simple, reliable means to evaluate therapeutic outcomes.¹⁸

7.4.7 Other Measures:

Local tissue water (LTW) measures will be obtained with a Moisture Meter D™ (Delfin Technologies, Finland). This device and technology has been demonstrated to provide a measure of LTW and its change based on measurements of the skin's tissue dielectric constant at a frequency of 300 MHz. The method has been widely used in clinical studies to evaluate LTW and its change under a variety of conditions.¹⁹⁻²² (Appendix E)

Interface pressure will be obtained with the PicoPress®. This technology was designed to be used to determine the pressure exerted under both static and dynamic compression. The PicoPress® transducer allows for dynamic pressures readings.²³ Appendix F

Symptom assessment will be obtained by using the Measure Yourself Medical Outcome Profile (MyMOP). This questionnaire was created to be a patient-generated or individualized outcomes questionnaire. It was designed to be problem specific but also include general wellbeing questions. Patient symptoms can be emotional, social or physical (Appendix G). At the conclusion of study treatment visits the subject-reported treatment comfort and effectiveness will be assessed by asking the subject targeted questions. (Appendix H)

Activity level will be monitored through the use of a pedometer and a subject diary. The subject wear a pedometer during the treatment phase of the study to record the number of steps accumulated throughout the day. The diary is intended to capture additional information regarding the subject's activity level such as type of activity.

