9.0 Safety and Adverse Events

9.1 Risk Analysis: The subjects enrolled in the study are not expected to be at any higher or additional risk than those who use non-study pneumatic compression devices. There is risk with using any pneumatic compression device. These may include, but are not limited to risk of explosion if the device is used in the presence of flammable gases, risk of electrical shock if

the device is immersed in water or if the housing is broken and subject attempts to service the unit.

Pneumatic compression devices are contraindicated for use in the presence of pulmonary edema, thrombophlebitis, congestive heart failure, deep vein thrombosis, episodes of pulmonary embolisms, acute cancer, acute infection, and inflammation or other conditions where increased lymphatic return is undesirable. Clinical trials have not been completed to show the safety of using the FT garments during pregnancy and therefore should not be used.

There are minimal side effects expected from the treatment subjects will receive in this study. The expected risks are often a failure to respond to the treatment intervention and are not related to the treatment itself. In some cases, side effects due to lymphoedema can be serious, long lasting, or may be permanent. The risks listed below are symptoms of lymphoedema and may be experienced by all subjects with lymphoedema:

Likely:

- Pain or discomfort
- Increased swelling

Less Likely:

- Cellulitis – Infection of the skin which may include swelling, redness, and tenderness of the infected tissue
- Development of or increased edema in the truncal and/or genital region.

Ultrasound, bio-impedance and moister meter are procedures with minimal risk involved.

9.2 Adverse Events Reporting: All adverse events (related or not related to the device treatment) that occur throughout the conduct of the study will be reported. An adverse event is defined as any undesirable experience associated with the use of a medical product.

Anticipated Adverse Events

Adverse events associated with lymphoedema may include, but are not limited to: cellulitis, deep vein thrombosis, increased swelling.

All adverse events are to be reported to TSTI at the time of occurrence or when the Investigator becomes aware of the adverse event (e.g., at the follow-up evaluation).

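### Truncal or genital oedema is a named risk but is not in the 5.3 safety check or the 9.2 list, and the trunk readings have no safety analysis

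*Combined protocol and SAP*

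**What the plan says.** **Risks and safety collection**

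- Section 9.1 lists four risks. One of the less likely ones is "Development of or increased edema in the truncal and/or genital region".
- Section 5.3 defines safety broadly ("Safety endpoints will include incidence and severity of complications") and then says what is looked for: "A clinician will assess any signs and symptoms of acute infection, DVT, cellulitis, pain or any other need for medical intervention".
- Section 9.2 requires every adverse event to be reported, whatever its relation to the device. Its open list of anticipated events reads "cellulitis, deep vein thrombosis, increased swelling".
- The table in 7.2 has an adverse-effects entry after treatment in each treatment-visit column, with no content specified.

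**Trunk measurements**

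- Section 7.4.5: "Tissue assessment/fibrosis will be evaluated with use of a tonometer at anatomically defined locations on the affected leg and on the trunk".
- Section 7.4.6: "Tissue ultrasound will be used to measure skin thickness and oedema in fixed areas of the limb and trunk". This is done before treatment on day 1, after treatment on day 5 in all groups, and on day 12 in Group A.

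**Analysis**

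- Section 8.2 ranks fluid dynamics first, tissue fibrosis second and patient-reported outcomes third. No safety outcome is ranked.
- Section 8.1 names ultrasound among the tissue measures, but 8.2.2 says that tonometry is the single method used and does not distinguish trunk sites from leg sites.
- Section 8 covers efficacy and adherence. It contains no safety analysis.

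**The concern.** The trial is meant to find the best of three regimens and to choose the primary endpoint for a larger trial. The outcomes ranked first describe fluid, led by bioimpedance, with local tissue water and limb volume alongside. A fall in leg volume looks the same whether fluid has been cleared or has moved proximally. Readings at the trunk are the scheduled data that could help to tell these apart, and the plan gives them no role in doing so.

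The clinical sign that would correspond to a proximal shift is the one risk in 9.1 that neither 5.3 nor 9.2 names. A general duty to report adverse events acts once an event has been noticed. Nothing in the supplied text directs staff to ask about or look for this one. If a regimen did shift fluid proximally, the leg result would favour it, and the plan has no by-arm result to set against that.

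**Working it through.** The plan states no event rate, power or alpha on this point and declares itself unpowered, so there is no figure to reproduce. The check is mainly a comparison of sections.

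**Step 1. The four risks in 9.1 against the other two lists**

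| Risk in 9.1 | Named in 5.3 | Named in 9.2 |
|---|---|---|
| Pain or discomfort | yes | no |
| Increased swelling | no | yes |
| Cellulitis | yes | yes |
| Truncal or genital oedema | no | no |

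Three of the four risks are named in at least one of 5.3 and 9.2. Truncal or genital oedema is the only one named in neither.

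**Step 2. What is collected at the trunk, and what section 8 does with it**

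| Measure | Day 5 reading in all groups | Separate trunk analysis | Safety use |
|---|---|---|---|
| Tonometry (7.2, 7.4.5) | yes | none; 8.2.2 does not split sites | none |
| Tissue ultrasound (7.2, 7.4.6) | yes | none; no ultrasound analysis in 8.2 | none |

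Both measures also have a pre-treatment reading on day 1, so a change to day 5 can be computed in every arm without new measurements.

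**Step 3. Exposure at the common day**

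The totals in 8.2 imply one hour per treatment: A 12 × 1 = 12, B 5 × 2 = 10, C 5 × 4 = 20 hours. By the end of day 5 the arms have received:

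- A: 5 × 1 = 5 hours
- B: 5 × 2 = 10 hours
- C: 5 × 4 = 20 hours

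Day 5 therefore compares the arms over the same calendar time at three levels of exposure. This is not evidence that harm rises with exposure. It shows only where a dose-related change could be examined.

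**Step 4. What event counts alone could show (event rates are assumptions)**

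Chance of at least one event in an arm of n = 10: 1 − (1 − p)^10.

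- p = 5%: 1 − 0.95^10 = 40.1%
- p = 10%: 1 − 0.90^10 = 65.1%
- p = 20%: 1 − 0.80^10 = 89.3%

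If the true rate were 10% and only half of the cases were noticed, the recorded rate would be 5% and the chance would fall from 65.1% to 40.1%.

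If no event is seen, the exact one-sided 95% upper bound is 1 − 0.05^(1/n):

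- 0 of 10: 25.9%
- 0 of 30: 9.5%

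Counts in arms of this size say little about an uncommon harm, and less if the harm is not solicited. The continuous trunk readings add information that counts cannot.

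**The case against.** The plan has real safeguards. Section 9.2 requires all adverse events to be reported, 7.2 collects adverse effects after treatment, 5.3 covers complications generally and ends with a catch-all, and 7.4.10 says that the subject is examined at the later treatment visits. Trunk tonometry brings staff into repeated contact with the trunk. MyMOP lets subjects nominate their own symptoms. All of this stands, and it rules out several stronger readings:

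- **A reader might infer that fluid moved to the trunk counts as benefit and never as harm.** It does not follow. A noticed event would be recorded, and no passage credits a rise in trunk fluid as benefit. Section 7.4.6 looks for trunk change without stating a direction.
- **A reader might infer that increased swelling is also left out of safety.** Section 9.1 lists "Increased swelling" and 5.3 does not, but 9.2 names it as anticipated, and limb volume is measured at each visit.
- **A reader might infer that the three lists contradict each other and must be identical.** The 9.2 list is expressly open and 5.3 has its catch-all, so differing examples are not a contradiction.
- **A reader might infer that the device displaces fluid proximally.** No passage shows this. Section 9.1 presents its listed risks as symptoms of lymphoedema, often reflecting non-response rather than the treatment.

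Two limits also stand. Tonometry responds to both pitting and fibrosis, so a change at the trunk has no clear direction of harm. The appendices with the tonometer body points, MyMOP and the interview questions are not in the supplied text, so a targeted question may exist there.

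The safeguards do not reach a mild or subclinical change. The 5.3 catch-all turns on a need for medical intervention, which mild swelling may not create. Whether such events reflect disease or dose can be examined only by comparing arms, and no such comparison is planned.

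**Conclusion.** The point holds in a limited form. One named risk is absent from both the 5.3 check and the 9.2 list, and two trunk measurements that are already scheduled have no separate or safety analysis. A clinically evident event would be captured. A mild or subclinical proximal shift could go unrecorded and uncompared between arms while the leg reduction is analysed as efficacy.

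The size of any harm cannot be stated, because the documents give no rate. At assumed rates of 5% to 20%, an arm of 10 would show at least one event 40.1% to 89.3% of the time with complete detection.

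The conclusion rests on displacement being a plausible concern, which the documents do not demonstrate, and on the appendices not already soliciting this risk, which cannot be checked. It does not undermine the design. It is a cheap improvement, and more than a wording matter because the trial is choosing between regimens.

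**What to change.** 1. In 5.3 and 9.2, name new or increased truncal or genital swelling.
2. In 7.2, add one targeted question on it to the existing adverse-effects entry.
3. In section 8, analyse trunk sites separately from leg sites. Report change in trunk ultrasound (skin thickness and oedema) and trunk tonometry by arm, descriptively, beside the study-leg volume result.
4. Compare arms at the common day 5. Group A's day 12 readings can be shown separately.
5. State that trunk tonometry has no unambiguous direction of harm, and that 10 subjects per arm allow estimation only.

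Section 7.1 says "Limb volume measures for both legs will be collected". Volume of the non-study leg may be reported descriptively, but should not be labelled a device safety result. In bilateral disease, 7.1 has that leg's prior treatment continue, whereas 7.4.8 withdraws home treatments other than garments and skincare at screening. Those two passages must be reconciled.

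The cost is wording in 5.3, 9.2 and section 8 and one case report form question. No visit, measurement or management rule is added. The downside is that solicited counts will run higher than volunteered ones, so they should not be compared with studies that relied on volunteered reports.
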